Study on the Gut Microbial Mechanism of
Negative Symptoms of Schizophrenia

Aug. 25th,2020

1. Subjects

Recruit 30 outpatient/inpatient schizophrenia patients (dominant negative symptoms) in Shanghai Mental Health Center (research group). At the same time, 15 cases of normal healthy people (control group) with similar eating habits and ages in the same region were matched.

Inclusion criteria:

- 1) 18-45 years old, Han nationality, no gender limit;
- 2) Meet the diagnostic criteria of "Schizophrenia" in the American Diagnostic 3) Standards for Mental Disorders (DSM-V);
- 3) The first attack, no antipsychotic drugs have been used in the past six months;
- 4) The PANSS negative symptom subscale has at least 3 items with 4 points and above or at least two items with 5 points and above, and the positive symptoms score is less than 19 points;
- 5) The negative symptom score is at least 6 points or more higher than the positive symptom score;
- 6) The cultural, social and educational background is sufficient to understand informed consent and research content.

Exclusion criteria:

- 1) Combined with DSM-V diagnosis other than schizophrenia;
- 2) G6 \geq 4 points in PANSS, or CDSS \geq 6 points;
- 3) SAS Side Reaction Scale $>$ 3 points;
- 4) Organic diseases of the central nervous system;
- 5) In the past two months, there were people who were dependent or abused on alcohol or other substances, which caused significant impairment of social and cognitive function;
- 6) In the past year, there have been major life events such as widowhood;

- 7) Serious suicide attempts;
- 8) The current patient's severe and unstable physical disease;
- 9) Pregnant and lactating women;
- 10) Have a history of antibiotic use of more than 3 days within 3 months;
- 11) Use probiotics (lactic acid products, etc.) for more than 3 days within 3 months;
- 12) Type 1 diabetes and severe diabetes complications;
- 13) Digestive system diseases such as gastrointestinal inflammation, acute or chronic hepatitis;
- 14) Severe organ diseases, such as cancer, coronary heart disease, myocardial infarction, cerebral hemorrhage;
- 15) Have infectious diseases, such as tuberculosis, AIDS;
- 16) Drug treatment of cholecystitis, peptic ulcer, urinary tract infection, acute nephritis, cystitis or hyperthyroidism.

Withdrawal criteria: Anyone who meets any of the following conditions at any time will terminate the study and complete all the evaluations originally scheduled for the 8th weekend:

- ① Those who did not meet the requirements of the group were found after joining the group;
- ② The patient or his legal guardian decides to withdraw from the study;
- ③ Serious adverse reactions occur, and the patients cannot tolerate them;
- ④ Serious physical diseases that may endanger the patient's life occur during the study, and the treatment should be terminated regardless of whether it is related to the study medication;
- ⑤ Those who do not use the medicine according to the study protocol, and have a follow-up period of 7 consecutive days or more than 7 days cumulatively;

⑥ Combined use of prohibited drugs or other treatment methods (including ECT, laser, cerebral circulation, brain function, etc.);

⑦ Other circumstances where the main researcher thinks it is necessary to terminate the research;

⑧ Lost to follow-up.

2. Calculation of sample size

Using (G*Power software to calculate, a 20% reduction rate for amisulpride treatment of negative symptoms is taken as the effective response, the first type of error α is 0.05, the second type of error β is 0.2, bilateral Test, the test power $1-\beta$ is 0.8. With reference to the previous literature using amisulpride to treat negative symptoms of schizophrenia, the statistical effect (effect size) is 0.98. This study conservatively estimates that the effect value is 0.8 for sample size calculation. After calculation, The required sample size is 26. According to 10% dropout, about 30 samples from the study group and 15 samples from the healthy control group are matched.

3. Methods

This study included patients with schizophrenia with dominant negative symptoms as the study group; the control group included normal healthy people with similar eating habits and ages in the same region.

1) Drug intervention method of the study group: The study group was given amisulpride tablets first. The initial dose was 50 mg/d. The doctor titrated the dose to the therapeutic amount within 1 to 2 weeks according to the patient's condition. The maximum dose was 300 mg/d, every day. Observe for 8 weeks. Instructions for the patient's use of other drugs: ① It is forbidden to use other antipsychotics, anti-anxiety drugs, other antidepressants or drugs that act on the

central nervous system (such as nootropics, drugs that improve cerebral circulation or brain metabolism, etc.) during the study and treatment); ② In principle, it is not advisable to combine other medications. For clinical needs (insomnia), non-benzodiazepine sleep aids (such as zopiclone, zolpidem, etc.) can be used first; short-term use of benzodiazepines is allowed , But avoid the use of drugs with long half-life such as clonazepam. Lorazepam or sulrazepam can be used for the purpose of improving sleep (single dose at night before going to bed), and should be stopped in time according to clinical conditions Use; ③ Allow the use of drugs to deal with adverse reactions, symptomatic or physical diseases (no pharmacological conflict with current medications), but the drug dose should be fixed as much as possible during the study period; ④ All combined medications must be recorded in detail.

- 2) Stool collection and processing in the study group: ① Time points for specimen collection: during the baseline period, 2 weeks of treatment, 4 weeks, and 8 weekends. ② Specimen collection method: save 5ml of fresh fecal specimens in the morning, use a dedicated sterile specimen box, collect the specimens under the supervision of a doctor or a trained family member, and immediately notify the designated person by telephone, put the specimens in a sterile EP tube and store them in Minhang Key Laboratory of Shanghai Mental Health Center-80 degree refrigerator. ③ The feces are collected and frozen in two parts. Part of it is reserved for flora analysis, using 16s amplicon sequencing technology to detect fecal DNA to understand the composition of intestinal flora, and the other part is retained.
- 3) Stool collection and processing in the control group: ① Time point of specimen collection: For the real world population, 5ml of fresh fecal specimens were collected at the time of enrollment, 2 weeks, 4 weeks, and 8 weeks after enrollment. ② Specimen collection method:

save 5ml of fresh fecal specimens in the early morning, use a special sterile specimen box, collect the specimens under the supervision of a doctor or trained healthy people, and immediately call the designated person, put the specimens into a sterile EP tube and store in Minhang Key Laboratory of Shanghai Mental Health Center-80 degree refrigerator. ③The feces are collected and frozen in two parts. Part of it is reserved for flora analysis, using 16s amplicon sequencing technology to detect fecal DNA to understand the composition of intestinal flora, and the other part is retained.

- 4) Blood specimen collection and processing: 10ml of fresh whole blood was collected at the time of enrollment, 2 weeks, 4 weeks, and 8 weeks after enrollment in the two groups. The blood specimens need to be centrifuged and processed using CBA (Flow Cytometry)) Detection of inflammatory factors (IL-1 β , IL-6, IL-10, TNF- α). The blood is tested for blood sugar and blood lipids at the same time.
- 5) Evaluation method: ①Evaluation time points: at baseline, 2 weeks, 4 weeks, and 8 weeks of treatment, respectively. ②Assessment content: assess the negative symptom scale scores of the Positive and Negative Syndrome Scale (PANSS), Calgary Depression Scale for Schizophrenia (CDSS), and clinical efficacy scale (Clinical Depression Scale for Schizophrenia). Global impression, CGI), Treatment Emergent Symptom Scale (TESS), Simpson Angus Rating Scale (SAS), Barnes Akathisia Rating Scale (BAS), followed by evaluation The patient's negative symptoms, depressive symptoms, efficacy and adverse reactions. ③ Special evaluators will be set up during the project implementation process, and the evaluators will independently evaluate the cases according to the established time nodes, and the evaluation results (efficacy, tolerability) will be fed back to the research doctor for drug

titration selection. The assessor is responsible for the assessment and filling of each CRF. The 8-week follow-up will be completed by the evaluator. ④ Research liaison: This project has set up a special research liaison who is responsible for the liaison work of this project, mastering the research number, and liaison with the evaluator and the research doctor. Follow-up method: According to the actual situation of the patient, this project can set the following 3 follow-up methods: follow-up in the hospital; follow-up at home (home visit); follow-up by telephone. Record each follow-up method in the CRF.

- 6) Other items: The two groups monitored Body Mass Index (BMI), abdominal circumference, heart rate, blood pressure, smoking and drinking, and psychoactive substance use before treatment and at the end of 2, 4, and 8 treatment.
- 7) Effectiveness evaluation index: The main evaluation index is the difference between the change of the intestinal microbial flora of the study group and the control group before and after treatment; the secondary evaluation index is the PANSS negative symptom scale score reduction rate $\geq 20\%$ as the effective group, observe the effective group and the ineffective group The difference in the changes of the intestinal microflora of the group; the correlation between the changes of the intestinal microflora of the effective group and immune factors and negative symptoms.

4. Statistical analysis

This experiment used SPSS19.0 software for statistical analysis. The measurement data adopts the mean \pm standard deviation, and the counting data adopts the rate or percentage. One-way analysis of variance was used to compare the two groups at baseline. The comparison of the study group before and after treatment used repeated measures analysis of variance. Changes in negative

symptoms, changes in immune factors and changes in intestinal flora composition were analyzed by PEARSON or SPEARMAN.

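### Sex is neither a matching factor for the 15 healthy controls nor in the only between-group test named, so the baseline patient-control comparison is open to confounding by sex

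*Combined protocol and SAP*

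**What the plan says.** The control group is described twice in the combined protocol and SAP. Section 1 (Subjects) states that "15 cases of normal healthy people (control group) with similar eating habits and ages in the same region were matched". Section 3 (Methods) repeats that "the control group included normal healthy people with similar eating habits and ages in the same region". Both name diet, age and region; neither names sex. Section 2 (sample size) says only "According to 10% dropout, about 30 samples from the study group and 15 samples from the healthy control group are matched", without listing factors.

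The first inclusion criterion is "18-45 years old, Han nationality, no gender limit", and no sex quota is set for patients or controls.

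Section 4 (Statistical analysis) gives one between-group method: "One-way analysis of variance was used to compare the two groups at baseline". It names no covariate and does not list the variables to be compared. The repeated-measures analysis is described for the study group only, and the remaining analyses are correlations.

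Under Section 3, stool, blood (four cytokines, glucose, lipids), BMI, abdominal circumference, smoking and drinking are collected in both groups at baseline and at weeks 2, 4 and 8. Item 7 there defines the main index as the between-group difference in flora change. The secondary indices are a comparison of effective with ineffective patients, and correlations within the effective group.

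**The concern.** Patients and controls are not randomised, so matching is the only stated protection against confounding. The plan accepts that principle for diet, age and region. Sex is left out of the same safeguard, and the analysis does not make up for it.

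Two mechanisms need to be kept apart. With 15 controls, chance can leave the groups unlike in sex even if both are drawn from populations with the same sex ratio. Separately, nothing ties the sex ratio of the controls to that of the patients, so recruitment could produce a systematic difference. In either case a baseline difference that reflects sex could be read as a feature of schizophrenia. If change over 8 weeks also differed by sex, a difference in change could be read as an effect of amisulpride.

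**Working it through.** **Inputs from the documents.** 30 patients and 15 controls; two-sided α = 0.05; sex absent from the matching factors and from the model.

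**Inputs assumed.** The documents give no sex ratio and no sex effect. I take the proportion male as 50% (range 30% to 70%) and the sex difference on an outcome as 0.2, 0.5 or 0.8 SD.

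**The plan's own figure.** The plan has no figure on sex balance. Its stated 26 is reproduced as the size per group of a two-sided, 1:1 two-sample t-test at effect 0.8 (power 0.807 at 26 per group, 0.791 at 25). The calculations below use the same kind of test at the planned 30 v 15.

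**Step 1: chance imbalance.** Let p₁ and p₂ be the observed proportions male. With a common source proportion p, the SD of p₁ − p₂ is √[p(1−p)(1/30 + 1/15)]. At p = 0.5 this is √(0.25 × 0.1) = 0.158, or 15.8 points. Summing the two exact binomials:

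- 50% male in both sources: P(difference ≥ 20 points) = 0.25; P(≥ 30 points) = 0.07.
- 30% or 70% male in both: 0.21 and 0.05.
- 50% v 60% male: P(≥ 20 points) = 0.34.
- 50% v 70% male: P(≥ 20 points) = 0.56.

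**Step 2: error rate given an imbalance.** Bias = sex difference × imbalance. In within-sex SD units the standard error is √(1/30 + 1/15) = √0.1 = 0.316. The rejection probability comes from the noncentral t with 43 df and noncentrality bias/0.316.

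| Assumed sex difference | Imbalance | Bias (SD) | Error rate |
|---|---|---|---|
| 0.2 SD | 20 points | 0.04 | 5.2% |
| 0.2 SD | 30 points | 0.06 | 5.4% |
| 0.5 SD | 20 points | 0.10 | 6.1% |
| 0.5 SD | 30 points | 0.15 | 7.5% |
| 0.8 SD | 20 points | 0.16 | 7.8% |
| 0.8 SD | 30 points | 0.24 | 11.5% |

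**Step 3: overall error rate.** The rates in Step 2 hold only once an imbalance has occurred. When both sources have the same sex ratio, sex is one more source of random variation and is already in the variance that the test uses. Simulating 30 v 15 from 50% male sources gives an overall rate of about 5% at 0.2, 0.5 and 0.8 SD. At 0.5 SD, the quarter of trials with an imbalance of 20 points or more reject at about 6.2-6.3%, and the rest at about 4.6-4.7%. These average to 0.25 × 6.2% + 0.75 × 4.6% = 5.0%, or 0.25 × 6.3% + 0.75 × 4.7% = 5.1%.

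The overall rate rises only if the sources differ. For 0.5 to 0.8 SD it is about 5.3-5.6% at 50% v 60% male, and about 6.0-7.5% at 50% v 70%.

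**Step 4: cost of adjusting.** With two thirds of subjects being patients and about half male overall, the squared correlation of group with sex is q² × (2/9)/0.25 for an imbalance q. At q = 0.20 this is 0.036, so the variance inflation is 1/(1 − 0.036) = 1.04. At q = 0.30 it is 0.08, giving 1/(1 − 0.08) = 1.09.

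**The case against.** A reader might infer from the table that the plan's false-positive rate is 6% to 11.5%. The documents do not support that. Those rates are conditional on an imbalance and on an assumed sex effect. Chance imbalance alone leaves the overall rate at about 5%, and an excess needs source populations that differ in sex ratio, on which the documents say nothing. At 0.2 SD the effect is negligible even given an imbalance. This objection stands.

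A reader might also infer that the main index is biased. It is a difference in change, so a fixed sex difference in level cancels. Bias there needs change over 8 weeks to differ by sex, and the documents offer no evidence that it does. The baseline comparison, where sex acts in full, is a step in Section 4 and not a named index. Nor is a patient-control cytokine comparison named: it is only implied by drawing blood in both groups, and the stated immune-factor analysis is a correlation within the effective group. Both secondary indices involve patients only, so the choice of controls cannot affect them. All of this stands and limits the weight of the point.

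Finally, leaving sex to adjustment would be a legitimate choice with 15 controls already matched on three factors. That is true, but Section 4 names no adjusted between-group model, so neither route is taken.

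**Conclusion.** The point holds in a limited form. Sex is controlled neither by design nor by analysis, and the baseline patient-control comparison of flora, and of blood markers if made, is exposed to it. The main index is exposed only through a sex difference in change; the patient-only indices are not exposed.

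The risk is mainly one of interpretation in the single trial that is run. Under equal source ratios there is about a one-in-four chance of an imbalance of 20 points or more, and a reader could not then separate sex from diagnosis at baseline. Inflation of the overall error rate is at most modest over the range examined (up to about 7.5%) and needs source sex ratios that differ. Every sex ratio and sex effect used here is an assumption. This is a cheap improvement to the design, not a flaw that invalidates it.

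**What to change.** Add sex to the matching factors in both places where the control group is described (Sections 1 and 3). Frequency-match the 15 controls to the patients, one control to two patients of the same sex where possible. This fits the planned 30:15 ratio: rounding to a whole control leaves at most half a control, 0.5/15 = 3.3 points, of imbalance. In Section 4, state that sex enters the between-group model where the match cannot be met, and report sex by group.

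The cost is a phrase in two places, one sentence in Section 4, and slightly slower choice of controls. If adjustment is used, the variance of the group contrast rises by a factor of about 1.04 to 1.09 at a 20 to 30 point imbalance. Matching has to be settled before the controls are chosen; after that, adjustment is the only remedy left.

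### Study-group change is tested by repeated-measures ANOVA with no stated time levels or missing-visit rule; a mixed model with dated exit evaluations is a cheap improvement

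*Combined protocol and SAP*

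**What the plan says.** Section 4 (Statistical analysis) states: "The comparison of the study group before and after treatment used repeated measures analysis of variance". It gives no levels for the time factor, no missing-data rule and no analysis population. The software is named: "This experiment used SPSS19.0 software for statistical analysis".

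Section 3 (Methods) schedules ratings, stool and blood at baseline and weeks 2, 4 and 8, and sets the treatment period: "Observe for 8 weeks". Item 5 also allows follow-up by telephone, which can supply ratings but not samples.

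Under the withdrawal criteria in Section 1 (Subjects), a patient who meets any criterion "will terminate the study and complete all the evaluations originally scheduled for the 8th weekend". The text does not say when this is done or which visit the values stand for. One of the listed reasons is "Lost to follow-up", where an exit evaluation may be unobtainable.

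Section 2 (Calculation of sample size) states "The required sample size is 26" and then "According to 10% dropout, about 30 samples from the study group".

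In Section 3, item 7, "the secondary evaluation index is the PANSS negative symptom scale score reduction rate" of at least 20%. This splits patients into effective and ineffective groups whose flora changes are compared. No status is given to a patient without a week-8 score.

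**The concern.** The plan foresees missing data but does not say what the analysis does with them. The two readings of the ANOVA lead to different problems.

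- **Four levels (the scheduled visits).** This is the natural reading, but it is not stated. Wide-format repeated-measures ANOVA keeps only patients with all four values. A patient who leaves before week 4 is lost even if an exit evaluation was done.
- **Two levels (before and after).** A missed middle visit does no harm. But an exit value from week 3, say, can enter as the after-treatment value.

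Several withdrawal reasons could be related to response: a decision by the patient or guardian, intolerable adverse reactions, not taking the medicine, and use of prohibited treatments. If leaving does depend on response, complete-case analysis biases the estimated change, in a direction set by who leaves. If it does not, there is no bias, but collected data are discarded. The responder split has a similar gap: if the status of patients without a week-8 score is settled after the data are seen, group membership becomes a choice.

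**Working it through.** **1. The plan's own figure.** Inputs from Section 2: two-sided alpha 0.05, power 0.80, effect size 0.8. Noncentral-t power for two independent equal groups is 0.791 with 25 per group and 0.807 with 26, so 26 reproduces as a per-group two-sample figure. Allowing for 10% dropout, 26/0.90 = 28.9, that is 29, consistent with about 30.

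**2. Power of the analysis at issue.** The study-group comparison is within patients. A paired t-test at a standardised change of 0.8 needs 15 patients (power 0.821).

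| Patients analysed | Paired power at 0.8 |
|---|---|
| 30 | 0.988 |
| 27 (30 × 0.90) | 0.979 |
| 25 | 0.970 |

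**3. Bias under the four-level reading.** The documents give no variances, so the model is assumed: 30 patients; visits at weeks 0, 2, 4 and 8; random intercept SD 1; slope mean −0.1 per week with SD 0.08; residual SD 0.5. Three patients (10%) leave after week 2 with no later value.

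- True week-8 change: 8 × (−0.1) = −0.80.
- SD of change: √(64 × 0.08² + 2 × 0.5²) = √0.9096 = 0.954.
- Standard error with 27 patients: 0.954/√27 = 0.18.

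"Moderate" means that the weight for leaving doubles per SD of poorer (or better) week-2 change. Complete-case means over 40,000 runs:

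| Who leaves | Estimate | Error | Error in standard errors |
|---|---|---|---|
| Unrelated to response | −0.80 | 0 | 0 |
| Poor early improvers, moderate | −0.833 | 0.033 (4%) | 0.18 |
| Good early improvers, moderate | −0.767 | 0.033 (4%) | 0.18 |
| The three poorest early improvers | −0.891 | 0.091 | 0.50 |
| The three best early improvers | −0.710 | 0.090 | 0.49 |

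A second assumed model had correlation 0.6 per 4 weeks, leaving after week 2 or week 4, and steeper selection of poor responders. At 10% dropout it gave an overstatement of about 8%, with 95% interval coverage of 0.93.

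**4. Bias under the two-level reading.** If 10% leave at random and a week-3 value counts as the end value: 0.90 × (−0.80) + 0.10 × (−0.30) = −0.75. For exits at weeks 5, 6 and 7 the same sum gives −0.77, −0.78 and −0.79.

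**5. What a mixed model does in the model of step 3, at 10% dropout.**

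- Categorical visit, unstructured covariance, scheduled visits only: −0.797 to −0.800.
- Actual week (linear and quadratic), random intercept and slope, exit value entered at week 3: −0.800 to −0.812 if the true course is linear, −0.780 to −0.794 if it levels off.
- Standard error about 0.18, as for complete cases, so there is no material gain in precision.
- If leaving depends on the unseen week-8 change: complete case −0.865, mixed model −0.849 to −0.856. There is almost no protection.

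In the second model, mixed-model bias was under 1%. Without a small-sample correction, coverage fell to about 0.93 in some runs.

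**6. Responder status.** At the planned dropout, up to 30 × 0.10 = 3 patients could lack a week-8 score.

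**The case against.** The strongest reply is that little is at stake. At the planned dropout the moderate-selection bias is under one-fifth of a standard error, precision is unchanged, and the model gives almost no protection where leaving depends on unseen values. All of this stands, and it limits the point to a cheap improvement.

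The withdrawal clause already answers part of the concern, since only patients who are lost or who refuse would have no end score. It can also be read as an evaluation at week 8 itself, in which case mis-timing does not arise. The wording allows either reading, so the date needs to be stated.

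A reader might infer three stronger conclusions. The documents support none of them.

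- **The study drops below its required size.** Expected completers are 27 against 26, so two more incomplete patients would leave 25. But 26 reproduces only as a per-group two-sample number, while the ANOVA criticised here is within patients and keeps power of 0.970 with 25. Falling below 26 shows no harm to this analysis.
- **The main index is biased by these amounts.** The main index compares flora change between study and control groups. The ANOVA covers the study group only, the figures are for an invented scalar outcome, and the flora bias cannot be quantified from the documents.
- **Patients without a week-8 score should count as non-responders.** The 20% rule is used to form groups for a flora comparison, not to report a response rate. That label would put patients of unknown response in the ineffective group.

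Nor do the documents support one particular random-effects structure. How a random-intercept model performs depends on the assumed slope SD, for which they give no figure.

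**Conclusion.** The point holds as a cheap improvement. As written, the plan either drops incomplete patients or can take an early exit value as the end value, and it does not say which. If leaving depends on early response, the complete-case change is biased: in the illustrative model at 10% dropout, by about 4% under moderate selection and by at most about half a standard error. A likelihood-based mixed model largely removes this when data are missing at random. Loss of power is negligible and is not part of the case.

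The sizes rest on assumed variances, trajectories and selection strengths, none of which are in the documents. They apply to scalar study-group outcomes only.

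**What to change.** 1. **Analysis.** For scalar study-group outcomes (PANSS negative score, cytokines, a diversity index), make the primary analysis a likelihood-based linear mixed model (SPSS MIXED, REML) on all available assessments. Pre-specify the covariance structure, a fallback if the model does not converge, and a small-sample degrees-of-freedom method. Report the week-8 change with its 95% confidence interval. Keep the repeated-measures ANOVA, with its time levels named, as a sensitivity analysis.
2. **Exit evaluations.** State when the withdrawal evaluation is done, record its date on the CRF, and analyse it at its actual week, not as week 8.
3. **Responder groups.** Define the 20% response at week 8 within a stated window. Leave patients without a week-8 score out of the effective-versus-ineffective flora comparison, and add a sensitivity analysis on how they are assigned.

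The cost is wording in Section 4, in the withdrawal paragraph and in Section 3 item 7, plus one date field on the CRF. No patients or visits are added, and SPSS is already the named software. The downsides are that the model assumes data missing at random, needs a covariance choice with 30 patients, does not protect against leaving that depends on unseen values, and leaves whole flora composition and the study-versus-control main index unaddressed.

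### Section 2's only power statement (80% at effect size 0.8, required size 26) is built on negative-symptom response, so it does not establish power for the primary flora-change comparison, and the size 26 does not match the planned 30 v 15

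*Combined protocol and SAP*

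**What the plan says.** Section 2 (Calculation of sample size) contains the document's only power statement. It sets "the first type of error α is 0.05", a two-sided test and power of 0.80. The outcome is clinical: "a 20% reduction rate for amisulpride treatment of negative symptoms is taken as the effective response". So is the source of the effect size: "With reference to the previous literature using amisulpride to treat negative symptoms of schizophrenia, the statistical effect (effect size) is 0.98". That value is then lowered: "This study conservatively estimates that the effect value is 0.8 for sample size calculation". The result is "The required sample size is 26. According to 10% dropout, about 30 samples from the study group and 15 samples" from healthy controls. Section 2 does not name the test, does not say whether 26 is per group or in total, and gives no reason for 15 controls.

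Section 3, item 7 ranks the outcomes. "The main evaluation index is the difference between the change of the intestinal microbial flora of the study group and the control group". This change is taken from pre-treatment to post-treatment. The 20% PANSS reduction appears one rank lower: "the secondary evaluation index is the PANSS negative symptom scale score reduction rate", used to separate responders from non-responders.

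Section 4 names one between-group test: "One-way analysis of variance was used to compare the two groups at baseline". It names repeated-measures analysis of variance for patients before and after treatment, and correlations. It names no test for the between-group difference in flora change.

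**The concern.** Two things do not line up. First, the outcome behind the sample size is not the primary outcome. An effect of a drug on symptom scores says nothing about how far flora change will differ between treated patients and untreated healthy people. Lowering 0.98 to 0.8 is cautious for symptoms only. Second, 26 looks like a per-group number for equal groups, while the plan enrols two patients for each control.

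Because the document offers a single power figure, it is easy to attach it to the main index. A null flora comparison could then be reported as coming from a study with 80% power, when the plan does not show that.

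**Working it through.** **Step 1: the outcomes side by side (no arithmetic).**

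| | Section 2 (power) | Section 3, item 7 (main index) |
|---|---|---|
| Outcome | negative-symptom response | change in gut flora |
| Effect size | 0.98 from literature, 0.8 used | none given |

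This mismatch stands whatever test produced 26.

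**Step 2: reproduce 26.** Inputs from Section 2: effect size d = 0.8, two-sided alpha 0.05, target power 0.80. For a two-sample t-test with group sizes n1 and n2, the noncentrality is λ = d × √(n1·n2/(n1+n2)) on n1+n2−2 degrees of freedom, and power is P(|T| > t_crit) under the noncentral t. For a paired or one-sample test, λ = d × √n on n−1 degrees of freedom.

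- Equal two-sample, 26 per group: λ = 0.8 × √(676/52) = 2.88, t_crit = 2.01, power 0.807. With 25 per group, power is 0.791. So 26 per group is the minimum.
- 26 as a total (13 v 13): power 0.499.
- Two to one: 38 v 19 gives 0.799 and 40 v 20 gives 0.819.
- Paired or within-patient: 14 gives 0.790 and 15 gives 0.821, so 15 suffices; 26 patients would give 0.975.

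Two near matches need inputs that contradict the text. 26 v 13 gives 0.802 at d = 0.98, but Section 2 says 0.8 was used. 30 v 15 gives 0.801 one-sided, but the test is stated to be two-sided.

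The dropout step is consistent for the patient group: 26/0.9 = 28.9, hence about 30.

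**Step 3: illustration at the planned sizes.** Assumptions, none of them in the plan: 0.8 carries over to flora change, there is one scalar measure, the groups are independent and there is no covariate adjustment. After 10% dropout, 30 × 0.9 = 27 patients and 15 × 0.9 = 13.5 controls, shown as 13 and 14 (and 15 if no control is lost).

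| Patients v controls | λ at d = 0.8 | Power at d = 0.8 | d for 80% power |
|---|---|---|---|
| 30 v 15 | 2.53 | 0.696 | 0.906 |
| 27 v 15 | 2.48 | 0.679 | 0.925 |
| 27 v 14 | 2.43 | 0.659 | 0.946 |
| 27 v 13 | 2.37 | 0.637 | 0.971 |

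Under these assumptions the chance of missing a difference of 0.8 is 1 − 0.696 = 0.30 to 1 − 0.637 = 0.36, against the 0.20 stated for the symptom outcome.

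**Step 4: sensitivity to baseline adjustment** (not in the plan; r is an assumed correlation between baseline and final value, with equal variances). If 0.8 is in units of the final-value SD, adjustment multiplies it by 1/√(1−r²). If it is in units of the change-score SD, the multiplier is √(2/(1+r)).

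| r | Scaling | Adjusted d | Power, 27 v 13 to 30 v 15 |
|---|---|---|---|
| 0.3 | final value | 0.839 | 0.68 to 0.74 |
| 0.3 | change score | 0.992 | 0.82 to 0.87 |
| 0.5 | either | 0.924 | 0.76 to 0.81 |
| 0.7 | change score | 0.868 | 0.71 to 0.76 |

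**The case against.** The strongest reply is that no calculation in Section 2 is shown to be wrong. It ties the 80% to symptoms and nowhere claims 80% for flora change or for 30 v 15. This is right. A reader might infer that the plan promises 80% for the main index and delivers 70%, but the documents do not support that: they make no such promise, and they give no flora effect size from which a true shortfall could be computed.

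A second reply is that 26 concerned patients only, with 15 matched controls added afterwards. The dropout arithmetic fits this reading, and an equal two-sample test of symptom response corresponds to no comparison in the plan, since the controls are healthy and untreated. On that reading 26 patients give 0.975 for a before/after test at 0.8. But 15 would have sufficed, so 26 is not explained, and a within-patient test would still not power a between-group index. What stands is that the origin of 26 is inferred, not documented.

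A third reply is that the 0.64 to 0.70 range depends on the analysis model. This also stands. Stool is collected at four time points in both groups, and Step 4 shows that with adjustment some admissible assumptions pass 80% at the planned sizes and others do not. Since Section 4 specifies no between-group analysis of change, none of these figures is the study's actual power.

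**Conclusion.** The power statement is wrong as written, as a mismatch of endpoint and allocation rather than a slip in calculation. The endpoint part rests on the text alone: the 80% was derived for negative-symptom response and does not establish power for the primary flora comparison, for which no power is shown at all.

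The allocation part is conditional. If 26 is per group, as its reproduction at 0.8 suggests, the 80% does not carry over to 30 v 15. The size of the gap, about 0.70 as enrolled and 0.64 to 0.68 after dropout, is an illustration that assumes d = 0.8 for one scalar flora-change measure compared without adjustment. On the same model, 80% power needs a standardised difference of about 0.91 (30 v 15) to 0.97 (27 v 13). It would go too far to conclude that the study is underpowered for flora change: the true effect, the measure and the test are all unspecified.

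**What to change.** No patients or procedures need to be added.

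- **Section 2, origin of 26.** Name the test and say whether 26 is per group or in total. If it is per group, state that 80% power does not carry over to 30 v 15.
- **Section 2, endpoint.** State that 0.8 comes from negative-symptom data and that the 80% is not the power for the main index.
- **Section 2, main index.** In place of the 80%, give the detectable difference. For example: with 27 evaluable patients and 13 to 15 controls, an unadjusted two-sample test of one prespecified scalar flora-change measure at two-sided alpha 0.05 has 80% power for a standardised difference of about 0.92 to 0.97.
- **Section 3, item 7, and Section 4.** Name that flora measure and that between-group test of change. Without this, the new sentence would describe an analysis the plan does not contain. If a different or baseline-adjusted analysis is chosen, recompute the figure for it and state the assumed correlation and the scaling of the effect.

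The cost is edits to three sections and a less favourable power statement.
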